10.1.9 Publication policy

The results for all primary and secondary outcome measures, irrespective of outcome, will be submitted by the sponsor for publication in academic journals. The results of this trial may also be presented by the sponsor at scientific meetings.

The results of this trial may be published or presented at scientific meetings by the investigator. If this is foreseen, the investigator agrees to submit all manuscripts or abstracts to the sponsor before submission. This allows the sponsor to protect proprietary information and to provide comments. The investigator will, on request, remove any previously undisclosed confidential information before disclosure, except for any trial treatment-related information necessary for the appropriate scientific presentation or understanding of the trial results.

Unless agreed in advance otherwise, site- or subpopulation-specific analyses may only be published after the outcomes of the primary endpoint analyses have been published.

The sponsor will comply with applicable requirements for publication of trial results. In accordance with standard editorial and ethical practice, including those established by the International Committee of Medical Journal Editors (ICJME). The sponsor will generally support publication of multi-site trials only in their entirety and not as individual site data. In this case, a coordinating investigator will be designated by mutual agreement.

Authorship will be determined by mutual agreement and in line with ICJME authorship requirements.

10.1.10 Protocol preparation and approval

This protocol has been prepared, reviewed and approved in accordance with the sponsor's standard operating procedures. Documentation of this process is filed in the trial master file.

10.1.11 Investigators and trial administrative structure

10.1.11.1 Investigators and trial site personnel

There must be an investigator at each trial site.

If the trial is conducted by a team of individuals at the trial site, the investigator leading and responsible for the team is called the principal investigator.

The responsibilities of principal investigator(s) must be documented before any trial-related procedure is performed. All persons assigned responsibility as principal investigator must sign a declaration of their responsibilities. They must also sign a declaration that they have read and understand the content of the protocol, that all questions have been adequately answered, and that they are qualified by experience and training to act as investigator for this trial.

The principal investigator at each trial site is responsible for ensuring that this trial is conducted in accordance with the protocol, the principles of GCP, and applicable regulatory requirements.

If the trial is conducted at multiple trial sites, a coordinating investigator must be assigned who is responsible for the coordination of investigators at different trial sites. The responsibilities of the coordinating investigator must be documented before any trial-related procedure is performed.

Documentation of all involved investigators must be maintained according to ICH GCP and applicable regulatory requirements.

Curriculum vitae and/or other relevant documents confirming the current qualification of the investigators must be provided to the sponsor. This should include any previous training in the principles of GCP, experience obtained from work with clinical trials, and experience with medical care.

10.1.11.2 Trial site personnel assigned trial-related duties

The principal investigator may define appropriately qualified personnel at a trial site to perform significant trial-related procedures and/or to make trial-related decisions under their supervision. In this case, the principal investigator must maintain a signed list of the persons to whom they delegate significant trial-related duties/responsibilities; the delegated trial-related duties/responsibilities must be specified in the list.

When personnel or responsibility changes are made, the principal investigator must ensure that the relevant documentation is updated before any trial-related activities are performed.

Documentation of all involved trial site personnel performing significant trial-related procedures and/or making trial-related decisions must be maintained according to GCP and applicable regulatory requirements.

10.1.11.3 Contract research organizations

Documentation of all involved CRO must be maintained according to GCP and applicable regulatory requirements. This includes documentation of any delegation of responsibilities to CROs.

10.1.11.4 The sponsor and sponsor's personnel

The trial sponsor listed on the title page accepts the responsibilities of the sponsor according to GCP and applicable regulatory requirements.

The sponsor will designate appropriately qualified personnel to advise on trial-related topics. The trial site will be provided with contact details for these personnel before any trial-related procedure is performed.

A list of key sponsor personnel involved in the preparation of this protocol and the conduct of the trial, including their full names, titles, roles, and responsibilities, will be maintained.

Some sponsor tasks may be delegated, e.g., to CRO staff. Documentation of any delegation of responsibilities will be maintained.

10.1.12 *Premature termination or suspension of the trial*

If the trial is prematurely terminated or suspended for any reason, the investigator should promptly inform the trial subjects, should assure appropriate therapy and follow-up for the subjects, and, where required by the applicable regulatory requirement(s), should inform the regulatory authorities. In addition:

If the investigator terminates or suspends a trial without prior agreement of the sponsor, the investigator should inform the institution where applicable, and the investigator should promptly inform the sponsor and the IRB/IEC and should provide the sponsor and the IRB/IEC a detailed written explanation of the termination or suspension.

Reasons for the early closure of a trial site by the sponsor may include (but are not limited to):

- Failure of the investigator to comply with the protocol, the requirements of the IRB/EC or local health authorities, applicable sponsor procedures, or the ICH GCP guidelines.
- Inadequate recruitment of trial subjects by the investigator.
- Discontinuation of further IMP development based on sponsor decision.
- If the trial is prematurely terminated or suspended, the sponsor shall promptly inform the investigators, the IECs/IRBs, the regulatory authorities, and any CROs used in the trial of the reason for termination or suspension, as specified by the applicable regulatory requirements. The investigator should promptly inform the trial subject and should assure appropriate therapy and/or follow-up (if applicable).

If the IRB/IEC terminates or suspends its approval/favorable opinion of a trial, the investigator should inform the institution where applicable and the investigator should promptly notify the sponsor and provide the sponsor with a detailed written explanation of the termination or suspension.

10.1.13 *Reporting of serious breaches*

A serious breach is any deviation from the approved protocol version that is likely to affect to a significant degree the safety of a trial subject and/or the rights of trial subjects and/or the reliability and robustness of the data generated in the clinical trial.

Trial sites, including pharmacists, CROs and other designees of the sponsor, must report any suspected serious breaches promptly to the sponsor. Suspected serious breaches, as well as any communication related to suspected serious breaches, must be reported to the sponsor by e-mail using the following e-mail address within 24 hours of knowledge:

- [REDACTED]

The sponsor will assess each suspected serious breach to decide whether it should be reported as a serious breach. The sponsor will comply with country-specific regulatory requirements relating to the reporting of serious breaches to regulatory authorities and IRBs/IECs.

10.2 Data collection and management

The trial documentation must be adequate for the reconstruction of the trial.

10.2.1 Data management

The CRO will be responsible for data management of this trial, including quality checking of the data.

Data entered manually will be submitted to the sponsor through use of an EDC system, data extracts, and reports. Trial sites will be responsible for data entry into the EDC system. In the event of discrepant data, the CRO will request data clarification from the trial sites, which the trial sites will resolve electronically in the EDC system.

The CRO will produce a Trial Data Validation Specification document that describes the quality checking to be performed on the data. CRFs and correction documentation will be maintained in the EDC system's audit trail.

System backups for data stored by the sponsor and records retention for the trial data will be in accordance with regulatory requirements.

At the end of the trial, the investigator will receive trial subject data for their trial site in a readable format that must be kept with the trial records. Acknowledgment of receipt of the trial subject data will be obtained.

10.2.2 Case report forms

CRFs will be completed through the use of an EDC system. Trial site personnel will receive training and have access to a manual for appropriate CRF completion. The CRFs should be handled in accordance with instructions and be submitted electronically to the sponsor via the system.

All CRFs should be completed by designated, trained trial site personnel. CRFs should be reviewed, verified, and then electronically signed and dated by the investigator or a designee.

10.2.3 Subject-reported outcomes

Subject e-diaries will be used for the reporting of reactogenicity (local and systemic reactions) by the trial subjects. See Section [8.2.5](#) for details (for e-diaries).

10.2.4 Investigator's Site File and the Trial Master File

The principal investigator is responsible for the filing of all essential documents in an ISF. The sponsor is responsible for the timely filing of all essential documents in the trial master file. As applicable, these files must be available at monitoring visits and during audits or regulatory inspections.

After trial completion, the principal investigator must ensure that all source data/documentation related to the trial is recorded, handled, and stored in a way that

allows its accurate reporting, interpretation and verification. The principal investigator must take measures to prevent accidental or premature destruction of these documents.

The principal investigator must keep the ISF, the source data/documentation arising from the trial according to the prescribed record retention period in the country and/or according to the hospital policy, but at least until informed by the sponsor that the trial-related records are no longer required.

10.3 Clinical laboratory tests

Blood/urine sampling for clinical laboratory tests will be performed at the time/days listed in the SoAs (Section 1.3 and Section 13.5).

The clinical laboratory tests are:

- Chemistry: alkaline phosphatase, alanine transaminase, creatinine, C-reactive protein, albumin, amylase, aspartate transaminase, gamma glutamyl transpeptidase, total bilirubin, indirect and direct bilirubin, blood urea nitrogen, glucose, lipase, cardiac troponin I.
- Hematology: hemoglobin, hematocrit, red blood cell count, white blood cell count and differential (absolute and %; neutrophils, lymphocytes, monocytes, eosinophils, basophils), platelet count.
 - Women who are VOCBP will be measured for serum β -HCG at Visit 0.
 - Women who are not VOCBP will be measured for follicle stimulating hormone (FSH) at Visit 0 (to confirm postmenopausal status).
- Dipstick urine analysis: glucose, bilirubin, ketone, specific gravity, blood, pH, protein, urobilinogen, nitrite, and leukocytes.
- Microscopic urinalysis: if warranted by dipstick results, urine sediment will be microscopically examined for the presence of red blood cells, white blood cells, casts, crystals, epithelial cells, and bacteria.

Additional tests may be performed (including the addition of parameters) at any time during the trial as determined necessary by the investigator or required by local regulations.

10.4 Adverse events: Definitions and procedures for recording, evaluating, follow-up, and reporting

10.4.1 ***Definition of AEs***

- An AE is any untoward medical occurrence in a trial subject administered a pharmaceutical product, which does not necessarily have to have a causal relationship with this treatment.
 - NOTE: An AE can therefore be any unfavorable and unintended sign (including an abnormal laboratory finding), symptom, or disease (new or exacerbated) temporally associated with the use of a medicinal product, whether or not considered related to the medicinal product.

10.4.1.1 **Events meeting the AE definition**

- Any abnormal laboratory test results (hematology, clinical chemistry, or urinalysis) or other safety assessments (e.g., ECG, radiological scans, vital signs measurements), including those that worsen from baseline, considered clinically significant in the medical and scientific judgment of the investigator.
- New conditions diagnosed after the date informed consent was given (ICF signed and dated) but before the first administration of trial treatment, that meet the criteria for SAEs.
- New conditions diagnosed after the first administration of trial treatment.
- Exacerbation of a chronic or intermittent pre-existing condition including either an increase in frequency and/or severity of the condition.
- Signs, symptoms, or the clinical sequelae of a suspected drug-drug interaction.
- Signs, symptoms, or the clinical sequelae of a suspected overdose of either trial treatment or a concomitant medication. Overdose *per se* will not be reported as an AE/SAE.

10.4.1.2 **Events not meeting the AE definition**

- (This trial will allow enrollment of healthy volunteers with pre-existing stable disease) Any clinically significant abnormal laboratory findings or other abnormal safety assessments which are associated with the underlying disease, unless judged by the investigator to be more severe than expected for the trial subject's condition.
- Medical or surgical procedure (e.g., endoscopy, appendectomy): the condition that leads to the procedure is the AE.
- Situations in which an untoward medical occurrence did not occur or continue (social and/or convenience admission to a hospital).
- New conditions diagnosed after the date informed consent was given (ICF signed and dated) but before the first administration of trial treatment that does not meet the criteria for an SAE.
- (This trial will allow enrollment of healthy volunteers with pre-existing stable disease) Anticipated day-to-day fluctuations of pre-existing disease(s) or condition(s) present or detected at the start of the trial that do not worsen.
- (This trial will allow enrollment of healthy volunteers with pre-existing stable disease) Disease-related events and/or disease-related outcomes not qualifying as AEs or SAEs are further specified in Section [8.3.7](#).

10.4.1.3 **Documentation of particular situations**

10.4.1.3.1 **AEs that are secondary to other events**

In general, AEs that are secondary to other events (e.g., cascade events or clinical sequelae) should be identified by their primary cause, with the exception of severe or serious secondary events. A medically significant secondary AE that is separated in time from the initiating event should be documented as an independent AE in source data and CRF. For example:

If vomiting results in mild dehydration with no additional treatment in a healthy adult, only vomiting should be documented as AE.

If vomiting results in severe dehydration, both events should be documented as AEs separately.

10.4.1.3.2 Abnormal laboratory results and vital signs values

Not every laboratory or vital signs abnormality needs to be documented as AE. For clinically significant laboratory/vital signs abnormalities the following definitions and documentation rules apply:

- If a laboratory/vital signs abnormality is a sign of a disease or syndrome, the laboratory/vital signs abnormality is clinically significant and only the diagnosis of the causing disease or syndrome needs to be documented as AE.
- If a laboratory/vital signs abnormality results in specific symptoms but no diagnosis of a disease or syndrome can be made, the laboratory/vital signs abnormality is clinically significant and only the symptoms need to be documented as AEs.
- If a laboratory/vital signs abnormality is not a sign of a disease or syndrome and does not result in specific symptoms but leads to a change in trial treatment or in a medical intervention, the laboratory/vital signs abnormality is clinically significant and must be documented as AE.

10.4.1.3.3 AEs associated with an overdose or error in drug administration

An overdose is the accidental or intentional use of a drug in an amount (per administration or cumulatively) higher than the dose being studied (for the trial treatment) or higher than the maximum recommended dose according to the authorized product information (for approved concomitant medications).

An error in drug administration is any administration outside what is foreseen in the protocol (higher or lower), including misuse and abuse of the product.

An overdose or incorrect administration of a drug is not itself an AE, but it may result in an AE.

All AEs associated with an overdose or incorrect administration of a drug should be documented as AE in source data and CRF and reported as SAE if applicable.

As of issue of protocol version 5.0, all cases of overdose or incorrect administration of a drug with or without AEs must be captured as AEs in the CRF as follows:

- If without an associated AE, as non-serious, related, Grade 1 AEs.
- If with an associated AE, as related with seriousness and grade corresponding to the associated AE.

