8.4 Procedures in case of overdose or errors in IMP administration

For a definition of an overdose and errors in IMP administration, see Section 10.4.1.3.3.
For the reporting of these events, see Section 10.4.1.3.3.

The sponsor does not recommend specific treatment for an overdose.

In the event of an overdose or an error in IMP administration, the investigator should:

- Contact the trial Medical Monitor immediately.
- (At the discretion of the investigator) Give symptomatic treatment.
- Closely monitor the trial subject for any AE/SAE and laboratory abnormalities (at least 7 d).
- Document the quantity of the excess dose as well as the duration of the overdose in the CRF.
- Document the error in IMP administration.

For cases of errors in IMP administration, the trial Medical Monitor, in coordination with the trial safety team, will decide on how the events should be captured in the database, and suggest appropriate corrective and/or preventive actions.

Decisions regarding dose interruptions or modifications will be made by the investigator in consultation with the trial Medical Monitor based on the clinical evaluation of the trial subject concerned.

[figure not shown]

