The relationship or association of an AE or SAE to a trial treatment/trial procedure will be assessed by the investigator after having evaluated all accessible data and, if necessary, he/she will re-evaluate the case as new information becomes available.

Events caused by the procedure of trial treatment administration should be differentiated from events caused by the trial treatment itself. Only events suspected to be caused by the IMPs itself should be documented as suspected adverse reactions but not events caused by the procedure of trial treatment administration.

In this trial, it cannot be excluded that during the course of the trial some procedures give rise to AEs which are related to the trial procedure and not to the trial treatment.

Procedure-related AEs occur during or after trial-specific procedure (e.g., discomfort after blood drawing) must be reported in the CRF on AE pages as “related to trial procedure” with the causing procedure specified. These procedure-related AEs should not include

events which correspond to solicited local reactions captured by subject e-diaries (these reactions, see Section 8.2.5.1).

Notes applicable for relationship to trial procedures including trial treatments

There may be situations in which an SAE has occurred, and the investigator has minimal information to include in the initial report to the sponsor. However, it is very important that the investigator always makes an assessment of causality for every event before the initial transmission of the SAE data to the sponsor.

The investigator may change their opinion of causality in light of follow-up information and send an SAE follow-up report with the updated causality assessment.

The causality assessment is one of the criteria used when determining regulatory reporting requirements.

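### Protocol 10.4.1.3.3 turns overdoses and administration errors with no associated event into related Grade 1 AEs, and SAP 6.5.1.3 counts them without separating them

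*Protocol*

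**What the plan says.** Protocol 10.4.1.3.3 opens with a definition: "An overdose or incorrect administration of a drug is not itself an AE, but it may result in an AE". It then sets a dated rule under which sites enter these cases as AEs: "As of issue of protocol version 5.0, all cases of overdose or incorrect administration of a drug with or without AEs must be captured". The entry takes one of two forms:

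- No associated event: "If without an associated AE, as non-serious, related, Grade 1 AEs".
- Associated event present: "If with an associated AE, as related with seriousness and grade corresponding to the associated AE".

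Three other protocol sections bear on the same cases:

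- **10.4.1.1** (events meeting the AE definition) says that overdose as such "will not be reported as an AE/SAE". It is silent on administration errors.
- **8.4** points to the rule ("For the reporting of these events, see Section 10.4.1.3.3"). For administration errors it also says that "the trial Medical Monitor, in coordination with the trial safety team, will decide on how the events should be captured in the database".
- **10.4.3** assigns causality to a person: "The relationship or association of an AE or SAE to a trial treatment/trial procedure will be assessed by the investigator".

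On the analysis side, having at least one AE up to 28 days after each dose is part of the primary objective (Protocol 3 and 13.6). SAP 6.5.1.3 summarizes AEs, related AEs and AEs by worst grade over that window. It contains no flag, exclusion or separate row for overdose or error records.

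**The concern.** An AE is defined in Protocol 10.4.1 as an untoward medical occurrence. A dosing error with no consequence is not one, and 10.4.1.3.3 says so before requiring that it be entered as one. Its relatedness and grade are fixed by rule and not by clinical judgement.

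The SAP tables are built from recorded AEs. If the rule is followed, a participant in whom nothing happened can be counted among those with an AE and among those with a related AE. The first is a primary safety rate; the second is the figure a reader uses to judge tolerability by dose level. In groups of 20 to 90, single participants are visible in these percentages.

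**Working it through.** The documents give no figure for this effect, so there is none to reproduce. The check sets the texts side by side and then works out what one case is worth.

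**1. Do the texts agree?**

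| Section | Overdose, no event | Administration error, no event |
|---|---|---|
| 10.4.1.1 | Not reported as an AE | Not addressed |
| 10.4.1.3.3, opening | Not in itself an AE | Not in itself an AE |
| 10.4.1.3.3, from v5.0 | Entered as an AE: related, Grade 1, non-serious | Same |
| 8.4 | Refers to 10.4.1.3.3 | Refers to 10.4.1.3.3, but capture also decided by Medical Monitor and safety team |

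They do not agree. For overdose the v5.0 rule conflicts with 10.4.1.1 and with its own opening. For administration errors it conflicts with its own opening, and 8.4 leaves open whether capture is fixed or decided case by case.

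**2. Would such a record fall in the counting window?** SAP 6.5.1.3 counts AEs from each dose to 28 days after it. Under SAP 6.1.4, an AE dated on a dosing day with no onset time is treated as post-dose. A record of a trial-vaccine dosing error would therefore normally be counted.

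**3. What does one case add?** SAP 6.1.1 divides the number of participants with the event by N in the analysis set. A participant with an error-only record and no other counted AE therefore adds 1/N to the any-AE rate. The same holds for the related-AE rate when there is no other related AE. Planned N comes from Protocol Table 6 and Table 2:

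- Cohort 5: 1/20 = 5.0 points
- One active group of 45: 1/45 = 2.2 points
- Cohorts 3a+3b or 4a+4b active: 1/90 = 1.1 points

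Two cases would add 2/20 = 10.0, 2/45 = 4.4 and 2/90 = 2.2 points; no case adds 0. The Dose 2 Safety Set may be smaller than planned N, which would make each case weigh more.

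**4. Illustration for the related-AE rate.** Assume no other related AE in the group, and use Clopper-Pearson 95% intervals. One error-only record changes the rate as follows:

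- N=20: from 0% (0 to 16.8) to 5.0% (0.1 to 24.9)
- N=45: from 0% (0 to 7.9) to 2.2% (0.1 to 11.8)
- N=90: from 0% (0 to 4.0) to 1.1% (0.0 to 6.0)

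**5. Which tables are not touched?** Error-only records are fixed as non-serious and Grade 1, so they cannot enter SAE or Grade ≥3 rows. The table of non-serious AEs above 5% is reached only if several participants share one preferred term: 2/20 = 10.0%, 3/45 = 6.7% or 5/90 = 5.6%.

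**The case against.** **The rule is only a CRF convention.** The v5.0 text is later and more specific, so it can be read as governing, with 10.4.1.1 left unaligned and 8.4 operating inside it. That reading is fair, but it does not remove the counting effect, because the tables use whatever is recorded as an AE. It also leaves text in 10.4.1.1 that needs correcting.

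**The inflation is hypothetical.** This stands. No number of errors is given, Protocol 6.4 has a second person confirm dose and subject at each administration, and 1/N is the weight of any single participant. Counting these records can only raise AE rates; it hides no harm. Preferred-term tables, AE listings, protocol-deviation summaries and listings and the treatment-administration listing would help a reader find cases. They would not change the overview rates.

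**Two stronger readings a reader might infer.** First, that the pre-set relatedness overrides the investigator on the associated event. The wording does not support this. What is captured is the case of overdose or error, and its grade and seriousness are taken from the associated AE as something separate. The natural reading leaves 10.4.3 in force for that AE.

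Second, that AE rates mix two recording definitions across cohorts. Cohorts 4a and 4b were added in v5.0, so of the 6 × 15 = 90 planned controls pooled in SAP 6.1, only 30 (33%) are certainly under the rule. That is a lower bound on coverage. The documents do not say whether earlier cases were entered retrospectively, so a mixture is possible but not shown.

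**Conclusion.** The concern holds as a minor point. The protocol texts conflict on whether an overdose or error without consequences is an AE. The SAP, applied as written, counts such a record in the any-AE rate, which is a primary safety summary, and in the related-AE rate.

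The size per case is 5.0, 2.2 or 1.1 percentage points at N = 20, 45 or 90. This assumes planned group sizes, a record dated within 28 days of a dose, and a participant with no other counted AE (or no other related AE, for the related rate). The total effect is unknown and may be nil.

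A reader should not conclude that reported rates are in fact inflated, or that the comparison of randomized arms within Cohort 4 is distorted: both arms there are under the same rule. No formal comparison between dose levels is planned.

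**What to change.** **Protocol.** Reconcile 10.4.1.1, 10.4.1.3.3 and 8.4 on whether and how these cases are recorded. State that the pre-set relatedness describes the error record while 10.4.3 governs the associated AE, or state otherwise if that is not the intention. Collection and safety reporting stay unchanged.

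**SAP 6.5.1.3.** Flag and list overdose and administration-error records that have no associated AE. If any occur, show them in a separate row and give the any-AE and related-AE overview rates with and without them. If none occur, a statement to that effect is enough; a duplicate set of all AE tables is not needed. Errors with an associated AE stay in all AE tables. Because the rule is dated from v5.0, note in the listing which records were entered under it.

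**Cost.** One derivation flag, to be checked against what the CRF records, a few conditional rows, and clarifying sentences in the protocol sections named.
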